4.1. Inclusion criteria

- BMI \geq 24kg/m²;
- 18 to 65 years old;

4.2. Exclusion criteria:

- Having any medical condition that would affect metabolism (i.e. diabetes, known hyperthyroidism or hypothyroidism);
- Myocardial infarction in the past six months;
- Heart failure (New York Heart Association III or IV);
- Uncontrolled hypertension (i.e. SBP>180 mmHg, and/or DBP >100 mmHg);
- Liver damage: total bilirubin >1.5× ULN(>34.2 μ mol/L(>2mg/dL) or AST and ALT >3× ULN (150U/L);
- Chronic kidney disease (serum creatinine >=1.5 mg/dL in men and >=1.3 mg/dL in women);
- Subjects suffered from acute or chronic gastrointestinal symptoms or had a history of gall bladder disease or biliary obstructive diseases in the past 30 days;
- Those allergies of proteins such as beans, wheat, milk;
- · Taking medication that would affect metabolism or weight loss (i.e. thyroid

medication and glucocorticoids) or anticipating a weight-loss program;

- Participating in weight loss programs currently or in the past 3 months;
- Currently pregnant or planning to be pregnant;
- Unable to participate in the follow-up examination.

5. Recruitment

Participants will be recruited from Guangdong province, China, from April, 2018. A total of 500 overweight/ obese adults aged 18-65 years old (BMI≥24kg/m²) from previous community screening programs will be invited to the near sub-center. Once a patient is confirmed to be eligible, the clinician will review the study procedures and requirements with the patient and discuss his or her commitment to the study and acceptance of randomization. Written informed consent will be obtained from each participant, and a baseline evaluation will be performed at the next visit, which is immediately scheduled by the clinician assistant.

6. Randomization and Masking

6.1. Randomization

Randomization will be conducted by Department of Bio-Statistics, Southern Medical University, China. Patients will be randomly assigned to NC group, LC diet group, CR diet group or LC+CR diet group using a block design. The randomization scheme is generated and concealed until an eligible participant is ready to be randomized. Prior to randomization, the study coordinator should confirm that all screening procedures have been completed, the participant meets all eligibility criteria, and all required baseline data have been collected. Any individual lacking required documents and data will not be randomized.

6.2. Masking

This is an open-label trial.

7. Intervention

This trial aims to test the effects of different diets on weight loss and metabolic risk factors. The duration of the intervention is 12 weeks.

7.1. Intervention programs

NC group

Participants in the NC group were designed to follow a non-restricted-calorie

diet with 55-65% of calories from carbohydrate, 30% from fat and 20% from protein[19, 31–32]. Participants will not be food choice restricted but they should avoid overeating. No specific exercise program will be recommended.

LC group

Participants assigned to the LC diet group were instructed to follow a non-restricted-calorie diet with less than 26% of calories from carbohydrates, 50% from fat and more than 24% from proteinc[15, 29-30]. Participants will receive free standard LC replacement, a nutritional bar (Nanda Fit Nutrition and Health Consulting Co., Ltd, Guangzhou, China) both at lunch and dinner (370kcal totally, specific formula shown in **Table 1**). Participants will not be food choice restricted but they should avoid overeating. Participants will be instructed to drink 2L water/day and to minimize fruits, bread, added sugars, refined white flour products, and sources of trans fats. No specific exercise program will be recommended.

CR group

Participants in the CR diet group were restricted daily calorie to 1,200-1,500kcal with 55-65% of calories from carbohydrate, 30% from fat and 20% from protein[29-30,32]. Participants will not be food choice restricted. No specific exercise program will be recommended.

LC+CR group

Participants assigned to LC+CR diet group were instructed to follow a daily calorie intake of 1,200-1,500kcal with less than 26% of calories from carbohydrate, 50% from fat and more than 24% from protein[29-31]. Participants will receive free standard LC replacement, a nutritional bar (Nanda Fit Nutrition and Health Consulting Co., Ltd, Guangzhou, China) at lunch and dinner (370kcal totally, specific formula shown in **Table 1**). Participants will not be food choice restricted and will be instructed to drink 2L water/day and to minimize fruits, bread, added sugars, refined white flour products, and sources of trans fats. No specific exercise program will be recommended.

Table 1. The Components of the Nutrition Food Bar

Content	Per 100 grams	NRV%
Energy	1723KJ	20
Protein	32.2g	54
Fat	15.7g	26

Trans Fatty Acids	0g	/
Carbohydrate	29.2	10
Meal Fiber	12.7g	51
Sodium	65mg	3

Master formula: whey protein, soy protein isolate, chia seed, oligosaccharide, Collagen, konjac extract, γ-aminobutyric acid.

NRV, nutrient reference values

Health education

All the participants will meet in weekly counseling sessions by dietitians to provide dietitian plans and give advice for 12 weeks. Guidance on counting macronutrients, reading nutrition labels and detailed dietary recipes will be given to four groups. All study participants were instructed to record macronutrients, nutrition labels and detailed dietary recipes all they consume whole day for 3 days per week, including 2 working days and 1 weekend day. Nutrient intake will be calculated based on the nutrient content listed in the Chinese Food Composition Table[33]. Furthermore, trial participants will be required to wear a Mi Band 2 Smart Bracelet (Xiaomi, Beijing, China) during the whole experimental process to record their regular physical activity. They were advised to do regular exercise 3 times a week with durations for 30 minutes. During each follow-up visit, participants will be asked about adverse reactions such as hunger, fatigue, palpitation, anorexia, constipation, alopecia. Research assistants will meet participants weekly to assess their compliance and provide advice on adherence to the diet program.

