7.2. Intervention monitoring and quality control

All the food consumption and exercise will be supervised by research assistants. The types of foods, amount of food and cooking methods, will be recorded by participants themselves. Nutrient intake will be estimated every 4 weeks, at baseline and 4-, 8- and 12-week. In order to reduce impacts caused by exercise, participants will be instructed not to change their daily physical activity and record their regular physical activity by wearing a Mi Band 2 Smart Bracelet (Xiaomi, Beijing, China) and record macronutrients, nutrition labels and detailed dietary recipes. Research assistants will call participants twice weekly to assess their compliance and provide advice on adherence to the dietary program. Adherence to the dietary program was

defined according to the number of days that a participant met the requirements of the assigned diet.

8. Study Outcomes

8.1. Primary outcome:

Changes in BMI from baseline at 12 weeks after intervention.

8.2. Secondary outcomes:

- Changes in body weight, waist circumference, WHR and body fat
- Changes in lipid and glucose
- Changes in insulin resistance
- Changes in urinary albumin and liver enzyme

9. Participant Termination and Retention

9.1. 9.1 Termination criteria

- Adverse events or other unexpected reasons (e.g., hypoglycaemia, constipation, gastrointestinal discomfort, etc.)
- Inability to complete required dietary program
- Unwillingness to be followed-up

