11.3. Week 0 visit (V2)

A. Exercise and dietary records will be reviewed.

B. Dietary evaluation and adjustment:

Participants will be asked to be as specific as possible about the type and amount(g/ml) of food and beverage consumed (e.g. skimmed or non-skimmed milk, 200ml), including type of cooking method used (e.g. roasted, boiled, etc.) by a 24-hour dietary recalls (3 days including two working days and one weekend day). Dietitians estimate and record the total intakes of calories(kcal), protein (%), fat (%), carbohydrates (%) according to the China Food Composition table.

C. Height, body weight, waist circumference, hip circumference, will be recorded at the end of every month.

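### The NC and CR macronutrient targets total 105-115% of calories, so no day can meet all three; as a separate minor item, the exercise advice conflicts with the instruction to keep activity unchanged

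*Protocol*

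**What the plan says.** **Diets.** In Protocol section 7.1 the CR arm is "restricted daily calorie to 1,200-1,500kcal with 55-65% of calories from carbohydrate, 30% from fat and 20% from protein". The NC arm has no calorie limit but the same shares: a "diet with 55-65% of calories from carbohydrate, 30% from fat and 20% from protein". Fat and protein are single values in both arms, with no wording such as up to or at least. The LC+CR arm is to have "less than 26% of calories from carbohydrate, 50% from fat and more than 24% from protein", and the LC arm has the same three figures.

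**Use of the targets.** Under Health education in 7.1, dietitians give plans, recipes and guidance on counting macronutrients to all four groups. At the week 0 visit (11.3), "Dietitians estimate and record the total intakes of calories(kcal), protein (%), fat (%), carbohydrates" as percentages. Section 7.2 says that adherence is "defined according to the number of days that a participant met the requirements of the assigned diet". No tolerance is given.

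**Exercise.** Each arm description in 7.1 ends with "No specific exercise program will be recommended". The Health education text then says of all participants: "They were advised to do regular exercise 3 times a week with durations for 30 minutes". Section 7.2 says: "In order to reduce impacts caused by exercise, participants will be instructed not to change their daily physical activity". Section 12.2 has the causality of adverse events judged against an exercise intervention, and 13.3 asks for data on a dropout's last exercise session.

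**The concern.** Shares of total calories from carbohydrate, fat and protein cannot exceed 100%. If the stated shares do, the diet cannot be delivered as written, and whoever plans it must decide which share gives way. The protocol does not say which. With 13 hospitals, different dietitians could settle it differently and still believe that they were following the text. A day count of adherence read literally on all three shares could also never be scored in NC or CR, although it could be in LC and LC+CR.

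The exercise wording raises a different question: whether a co-intervention that 7.2 sets out to hold constant is in fact being changed by the trial's own advice. The wording in 12.2 adds a safety aspect. Section 12.4 counts only events rated definite or probable, so it matters that causality is judged against the intervention under test, which is diet.

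**Working it through.** The protocol states no total for the shares, so there is no figure to reproduce. All inputs are from section 7.1 unless noted.

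**Step 1. Sum of the NC and CR targets** (carbohydrate + fat + protein):

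- at 55% carbohydrate: 55 + 30 + 20 = 105%
- at 60%: 60 + 30 + 20 = 110%
- at 65%: 65 + 30 + 20 = 115%

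Fat and protein together take 30 + 20 = 50%. That leaves 100 - 50 = 50% for carbohydrate, below the 55% floor. No value in the range works.

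**Step 2. Same check for LC and LC+CR.** With fat at 50%, carbohydrate and protein share the other 50%. Carbohydrate below 26% then means protein above 24%, so the two limits agree. For example, 25 + 50 + 25 = 100%.

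**Step 3. The excess in CR energy terms** (share × daily limit):

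- at 1,200 kcal: 1,200 × 0.05 = 60 to 1,200 × 0.15 = 180 kcal/day
- at 1,500 kcal: 1,500 × 0.05 = 75 to 1,500 × 0.15 = 225 kcal/day

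This is the amount by which the targets fail to fit together. It is not energy that anyone is told to eat.

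**Step 4. Ways a planner could absorb it**, with carbohydrate kept in range:

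| Excess taken from | Fat (stated 30%) | Protein (stated 20%) |
|---|---|---|
| Fat only | 25% down to 15% | 20% |
| Protein only | 30% | 15% down to 5% |
| Both equally | 27.5% down to 22.5% | 17.5% down to 12.5% |

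The first figure in each pair is for 55% carbohydrate, the second for 65%.

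**Step 5. Tolerance needed to make a day scorable.** If all three shares may flex, the smallest uniform tolerance is 5 / 3 = about 1.7 points, giving roughly 53.3 / 28.3 / 18.3. If carbohydrate must stay in range and only fat and protein flex equally, it is 5 / 2 = 2.5 points at 55% and 15 / 2 = 7.5 points at 65%.

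**Step 6. Exercise statements side by side.** The Health education advice amounts to 3 × 30 = 90 minutes a week. The 7.2 instruction is to leave daily activity as it was. A participant not already exercising at that level cannot follow both. The arm descriptions rule out only a specific program. Advice that names a frequency and duration but no type or intensity need not be one.

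**The case against.** **Fat and protein may have been meant as upper limits.** That reading would make the targets feasible. But the text does not say it, and the same section uses limit wording for LC and LC+CR. Read as ceilings, the targets would also admit 65 / 30 / 5, that is 5% protein. The text needs correcting on either reading.

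**A dietitian can plan near 55% carbohydrate, and a small tolerance resolves the rest.** This stands in part. The 15-point excess arises only at the top of the range, and at 55% about 1.7 points on each share is enough. But the protocol states no tolerance, and 65% is an allowed target.

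**A reader might infer that adherence is zero by construction in NC and CR and so biased between arms.** The document does not go that far. Section 7.2 refers to the requirements of the assigned diet without saying that all three shares must be met exactly. The 50% fat share in LC and LC+CR would need a tolerance in practice too. Adherence is not an outcome in 8.1 or 8.2, nor a term in the model in 16.2.

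**A reader might infer that the BMI comparison is compromised.** It is not. The analysis follows the randomized assignment. The intended contrast of 55-65% against less than 26% carbohydrate remains, as does the 1,200-1,500 kcal limit. Uneven delivery across sites is a possibility that the text leaves open, not something shown.

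**A reader might infer that the exercise advice flatly contradicts 7.1.** General advice under Health education sits awkwardly with the arm descriptions but does not strictly contradict them. The direct conflict is with 7.2. The advice goes to all four arms, so no between-arm bias follows from it. References elsewhere to supervised exercise can be read as monitoring, since the bracelet records ordinary activity.

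**Conclusion.** The diet point holds and should be fixed. As written, the NC and CR targets exceed 100% of calories by 5 to 15 points, so two of the four assigned diets cannot be delivered on all three shares. This is an error in the definition of the intervention, not a detail left for later. It rests only on addition and on taking fat and protein as the point values that the text gives. The consequence is limited to how uniformly those two diets are delivered and how their adherent days are scored.

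The exercise point holds as a separate minor item. The 90 minutes a week of advice conflicts with 7.2 for anyone not already at that level, and 12.2 and 13.3 refer to exercise where the intervention under test is diet. No effect on BMI is shown.

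**What to change.** **Diets.** Restate the NC and CR targets as ranges with floors that can total 100%. An example, with values to be confirmed by the clinical team, is carbohydrate 55-65%, fat 20-30% and protein 15-20%. The floors sum to 55 + 20 + 15 = 90 and the ceilings to 65 + 30 + 20 = 115. At each carbohydrate value from 55% to 65%, fat plus protein must supply 45% down to 35%, which lies within their combined range of 35-50%. So 55 / 30 / 15, 60 / 20 / 20 and 65 / 20 / 15 all fit, although at 65% carbohydrate the last is the only split. The protein floor equals 1,200 × 0.15 / 4 = 45 g/day at 1,200 kcal and 1,500 × 0.15 / 4 = about 56 g/day at 1,500 kcal, assuming 4 kcal per gram.

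**Adherence.** In 7.2, score adherent days in all four arms against the corrected targets, with one stated tolerance.

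**Exercise.** Delete the three-times-a-week advice so that 7.2 governs. Keeping the advice and amending 7.2 would also be consistent, but would give up the stated aim of limiting the influence of exercise. In 12.2, change the exercise intervention to the dietary intervention. In 13.3, ask for the last dietary record instead of the last exercise session.

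**Cost.** A protocol wording correction and a memo to the sites. The design, sample size and analysis do not change.

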7.2. Intervention monitoring and quality control

All the food consumption and exercise will be supervised by research assistants. The types of foods, amount of food and cooking methods, will be recorded by participants themselves. Nutrient intake will be estimated every 4 weeks, at baseline and 4-, 8- and 12-week. In order to reduce impacts caused by exercise, participants will be instructed not to change their daily physical activity and record their regular physical activity by wearing a Mi Band 2 Smart Bracelet (Xiaomi, Beijing, China) and record macronutrients, nutrition labels and detailed dietary recipes. Research assistants will call participants twice weekly to assess their compliance and provide advice on adherence to the dietary program. Adherence to the dietary program was

defined according to the number of days that a participant met the requirements of the assigned diet.

8. Study Outcomes

8.1. Primary outcome:

Changes in BMI from baseline at 12 weeks after intervention.

8.2. Secondary outcomes:

- Changes in body weight, waist circumference, WHR and body fat
- Changes in lipid and glucose
- Changes in insulin resistance
- Changes in urinary albumin and liver enzyme

9. Participant Termination and Retention

9.1. 9.1 Termination criteria

- Adverse events or other unexpected reasons (e.g., hypoglycaemia, constipation, gastrointestinal discomfort, etc.)
- Inability to complete required dietary program
- Unwillingness to be followed-up

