12.5. Assessment of severity

The severity of adverse events is categorized at three levels as follows:

Mild: usually temporary and not affecting daily activities.

Moderate: causing discomfort and affecting daily activities, though tolerable and not requiring participants to take any medication.

Severe: disrupting daily activities and intolerable, requiring participants to take medication immediately.

Treatment Physicians will observe and record the progress of adverse events and keep track of those participants who have dropped out until the adverse events have completely subsided. Additionally, physicians will evaluate those adverse events for a causal-effect relationship.

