13.1. Dropout determination

Participants who withdraw from the trial for any reason will be considered a drop-out.

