13.2. Common reasons for dropping out

- Poor compliance with the protocol
- Adverse events
- Lack of efficacy
- Withdraw and quit
- Others

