13.3. Dropout management

Physicians should complete the case report form and record the reason for dropping out. Physicians should also assess the causal-effect relationship of the intervention with adverse events and collect detailed data related to the last exercise session. The data from subjects who have dropped out will be stored and used for intention-to-treat analysis

14. Ethical requirements

The study followed the ethical guidelines of the Helsinki Declaration and obtained the approval of the Ethics Committee of Zhujiang Hospital of Southern Medical University (ratification No.:2018-NFMDXK-001), the host research unit, and complete registration at the China Clinical trial Registration Center (registration number: ChiCTR1800015156).

15. Data management

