15.3. Data reports

Several standardized reports will be generated as follows: 1) participant recruitment and follow-up; 2) demographics; 3) data quality and monitoring; 4) adverse events. These reports will be used for study management. These reports will be blinded to research personnel who collect study outcomes.

16. Data Analysis Plan

Data will be analyzed according to participants' randomization assignments, regardless of their subsequent status (intention-to-treat).

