16.2. Analysis methods

Data will be analyzed according to participants' randomization assignment (intent-to treat). A mixed-effects model will be used to assess the effects of diet programs on the change in BMI and an autoregressive correlation matrix will be used to correct within-participant correlation for repeated measurements. In this model, variables will be assumed to be random effects, and intervention group, time, and their 2-factor interactions, age, sex will be assumed to be estimable fixed effects. PROC MIXED of SAS statistical software, version 9.4 (SAS Institute Inc), will be used to obtain point estimates and SEs of the treatment effects and to test for differences between treatments. Multiple imputations for missing data in the multivariable analyses will be conducted using the Markov chain Monte Carlo method. P-value <0.05 will be considered as statistically significance. Group differences in the study outcomes will be evaluated using the general linear model for continuous variables and the chi-squared test for categorical variables. Data will be presented as least-squares means with 95% confidence intervals (CIs).

17. Training for Study Staff

All study staff (physicians and nurses) will be trained and certified before the study is initiated. The training program will include instruction on questionnaire administration and anthropometrics (height, weight, waist circumference, and hip girth) and blood pressure measurement. A standard questionnaire will be used, which includes personal information (name, sex, age, place of birth, marital status, occupation, education, household income, etc.), medical history, medication use, family history, lifestyle factors (smoking and drinking), physical activity, dietary habits, and menstrual and reproductive history. Anthropometric measurements and blood pressure will be obtained using a standard protocol. The data, including that for dietary record, duration, heart rate, and anthropometric measurements, will be collected and recorded in CRFs by research assistants every week. Body fat mass will be quantified using a body composition analyzer (Jawon Medical, Gyeongsansi, South Korea). All technologists are experienced and blind to randomization of the participants.

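### Section 9.1 ends participation for diet failure without keeping those people on BMI follow-up, which conflicts with an intention-to-treat analysis regardless of later status

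*Protocol*

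**What the plan says.** Section 9.1 of the protocol, under the heading on participant termination and retention, lists three termination criteria: adverse events or other unexpected reasons, "Inability to complete required dietary program", and "Unwillingness to be followed-up".

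Section 13.1 defines drop-out broadly: "Participants who withdraw from the trial for any reason will be considered a drop-out". Section 13.2 gives "Poor compliance with the protocol", adverse events and lack of efficacy among the common reasons.

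On what happens afterwards, section 12.5 has physicians "keep track of those participants who have dropped out until the adverse events have completely subsided". Section 13.3 asks for the reason, a causality assessment and details of the last session, and adds: "The data from subjects who have dropped out will be stored and used for intention-to-treat analysis".

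Section 16 opens with the analysis principle: "Data will be analyzed according to participants' randomization assignments, regardless of their subsequent status (intention-to-treat". Section 16.2 specifies a mixed-effects model with group, time, their interaction, age and sex, and adds: "Multiple imputations for missing data in the multivariable analyses will be conducted using the Markov chain Monte Carlo method".

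The primary outcome (section 8.1) is change in BMI from baseline to 12 weeks. Sections 11.4 to 11.6 schedule height and weight at weeks 4, 8 and 12.

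**The concern.** An intention-to-treat analysis that ignores later status needs the outcome on people whatever happens to their diet. Section 9.1 works the other way: failing the diet, or having an adverse event, is itself a reason to end participation. Because refusal of follow-up is a separate item in that list, the other two criteria can remove people who would have been willing to be weighed.

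If their week-12 BMI is not taken, missingness depends on adherence and tolerability after randomisation. The mixed model and multiple imputation ordinarily rest on missing at random. Without weights taken after stopping, they have little from which to learn what happens to BMI once the diet is abandoned, so the estimate drifts towards the effect in people who stay on the diet. This is bias, and a larger sample would not remove it. Nor could a statistical analysis plan recover weights that were never taken.

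**Working it through.** **1. What the protocol provides after termination or drop-out**

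| Item | Provided? | Where |
|---|---|---|
| Reason recorded | Yes | 13.3 |
| Causality and last-session details | Yes | 13.3 |
| Tracking until adverse events subside | Yes | 12.5 |
| Existing data stored and used | Yes | 13.3 |
| BMI at the remaining visits | Not stated | none |

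Stopping the diet and leaving the study are not distinguished anywhere in sections 9.1 or 13. Section 16 assumes that they are.

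**2. The plan's own drop-out figure**

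Section 3.2 inflates 60 per group for 20% drop-out: 60 / (1 - 0.20) = 75 per group, and 4 x 75 = 300. This step reproduces. Twenty per cent of 75 is 15 people per arm. (The 60 does not follow from the printed effect and standard deviation, but that is a separate matter and nothing here depends on it.)

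**3. Illustration of the size**

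Inputs:
- Effect of -0.6 kg/m2, from section 3.2. It is treated here as the effect of a diet against NC among people who stay on the diet, with the NC mean taken as unaffected.
- d = share of a diet arm terminated for stopping the diet. The protocol does not give it; 5%, 10% and 20% are assumed. The top value equals the whole planned drop-out.
- r = share of the effect that these people keep at week 12. The protocol does not give it; 0 and 0.5 are assumed.
- Imputation is assumed to return -0.6, that is, to learn nothing from the terminated participants' earlier visits.

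Formulas:
- Intention-to-treat effect = -0.6 x [(1 - d) + d x r]
- Overstatement = 0.6 x d x (1 - r)

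| d | r | Intention-to-treat effect | Overstatement (kg/m2) | As % of that effect |
|---|---|---|---|---|
| 5% | 0 | -0.570 | 0.030 | 5.3% |
| 5% | 0.5 | -0.585 | 0.015 | 2.6% |
| 10% | 0 | -0.540 | 0.060 | 11.1% |
| 10% | 0.5 | -0.570 | 0.030 | 5.3% |
| 20% | 0 | -0.480 | 0.120 | 25.0% |
| 20% | 0.5 | -0.540 | 0.060 | 11.1% |

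For example, at d = 20% and r = 0: -0.6 x 0.80 = -0.48; 0.60 - 0.48 = 0.12; 0.12 / 0.48 = 25%. At r = 1 the overstatement is zero for every d.

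**The case against.** The strongest reply is that no sentence says outcome visits stop. Section 9.1 does not say whether the diet, the study or follow-up ends. The week 4, 8 and 12 weighings are not made conditional on adherence, section 9.2 promises effort to keep people on the visit schedule, and section 13.3 uses drop-outs' data. This stands to the extent that loss of week-12 BMI is an inference. It does not remove the problem: the list is one of termination criteria, the only tracking stated after drop-out concerns adverse events, and a general retention effort does not override a termination rule. Thirteen hospitals will have to apply the wording as it is.

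A reader might go further and infer that non-adherers' week-12 values are lost and filled in as if they were still on the diet, to the advantage of the stricter diets. The documents do not support that much:
- Section 13.2 describes common reasons for dropping out. It is not a rule that removes people for poor compliance or lack of efficacy.
- Section 7.2 defines adherence by the number of days on which the diet was met, so partial adherers can stay in and inform the model.
- BMI recorded at weeks 4 or 8 before stopping would soften the bias, and the details of the imputation model may properly sit in a statistical analysis plan.
- One drop-out rate is given for all groups, and NC also has a prescribed diet. Unequal loss is plausible, because NC is the least restrictive arm, but it is not documented.
- The effect can be estimated under missing at random. What is in doubt is whether that assumption is credible here.

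The 20% is also an all-cause figure. It includes people who refuse follow-up, whom no change of wording would recover.

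**Conclusion.** The point holds as a conflict between sections 9.1 and 13 on one side and section 16 on the other. As written, diet failure or intolerance after randomisation can determine who contributes a week-12 BMI, and nothing keeps willing participants on the weighings. It should be corrected because it bears on the primary outcome and data not collected cannot be restored.

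The size is uncertain. Under the assumed inputs the overstatement is about 0.015 to 0.12 kg/m2, roughly 3% to 25% of the intention-to-treat effect. The 0.12 is an upper bound for this illustration: it needs all of the planned 20% drop-out to come from stopping the diet, none of the effect to be kept, and earlier visits to be uninformative. If the effect is fully kept there is no bias. Any difference in its direction or size between the diet arms is conjecture on this text.

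**What to change.** Reconcile sections 9.1, 13 and 16:

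- Record two separate statuses: stopped the assigned diet, and withdrew from follow-up.
- State that participants who stop the diet, for whatever reason, but do not withdraw consent to follow-up are still weighed at the scheduled week 4, 8 and 12 visits and analysed in their randomised arm.
- Reserve drop-out, for the purpose of missing outcome data, for those who leave follow-up.

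A sensitivity analysis for the outcomes that remain missing can be left to the statistical analysis plan.

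The cost is the change of wording, some effort to keep these participants attending visits that are already in the schedule, and an estimated effect that may be smaller. No view is taken on when a diet should be stopped; that remains with the clinical team.
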